11.0 Risks and Benefits	17
11.1	17
Physical, Functional, Range of Motion Testing	17
11.2 Blood Flow Restriction device	17
11.3 DEXA Scan	18 17
11.4 InBody Bioelectrical Impedance scan	18
11.5 Confidentiality	18
11.6 Data Safety Monitoring Plan	18
12.0 Ethical Considerations.....	18
13.0 References	19

Use of Blood Flow Restriction + Standard of Care Physical Therapy to Improve Functional Outcomes after
Anterior Cruciate Ligament Reconstruction
PI: [name].
Institution: UAMS
Sponsor: UAMS

List of Abbreviations

ACL	Anterior cruciate ligament
BFR	Blood Flow Restriction
CRF	Case Report Form
DEXA	Dual-energy X-ray Absorptiometry
EMR	Electronic medical record
FDA	Food and Drug Administration
IRB	Institutional Review Board
MVC	Maximal voluntary contraction (of the quad muscles)
NIH	National Institutes of Health
PBFR	Personalized Blood Flow Restriction
PT	Physical Therapist
RIOA	Reynolds Institute on Aging
ROM	Range of Motion (of the knee joint)
UAMS	University of Arkansas for Medical Sciences
UPIRTSO	Unexpected problem involving risks to subjects or others

Study Schema

Surgeon collaborators or their designees screen their orthopedic clinic for eligible subjects and send referrals to study staff via UAMS email.

Study staff contact referrals via phone or email to discuss consent process.

Visit 1: Subjects come to RIOA for informed consent process prior to surgery.
Randomization (1:1) occurs.

Visit 2: Approx. 7-10 days prior to surgery, subjects come to RIOA for baseline testing.

Subjects undergo scheduled knee surgery at UAMS

***Prescribed physical therapy begins with or without BFR per randomization at UAMS
Colonel Glenn facility***

Visit 3: Subjects come to RIOA for post-operative testing approx. 8 weeks postop.

Prescribed physical therapy continues with/without BFR per randomization

Visit 4: Approx. 12 weeks postop, subjects come to RIOA for mid-point testing.

Visit 5: Approx. 16 weeks postop, subjects come to RIOA for end-point testing.

Use of Blood Flow Restriction + Standard of Care Physical Therapy to Improve Functional Outcomes after
Anterior Cruciate Ligament Reconstruction
PI: [name].
Institution: UAMS
Sponsor: UAMS

Study Calendar

Procedure	Visit 1	Visit 2	Visit 3	Visit 4	Visit 5
Informed consent	X				
10-meter walk test		X	X	X	X
bilateral MVC		X	X	X	X
DEXA scan		X	X	X	X
In Body scan		X	X	X	X
Stair ascent			X	X	X
Stair descent				X	X
Y-balance test			X	X	X

1.0 Protocol Summary

This will be a randomized pilot study to determine the effectiveness of Personalized Blood Flow Restriction (PBFR) technique in conjunction with prescribed physical therapy (PT) in a cohort of anterior cruciate ligament (ACL) reconstruction subjects. Both groups of subjects will undergo unilateral ACL reconstruction at University of Arkansas for Medical Sciences (UAMS), followed by prescribed PT at the UAMS Orthopedic Clinic at Colonel Glenn.

Up to 25 subjects will be enrolled. Half are randomized to the BFR group with the other will perform PT without BFR.

Data collection will occur at four approximate occasions: pre-surgery, 8-weeks postop, 12-weeks postop, and 16-weeks postop.

2.0 Background

Anterior cruciate ligament tears are a costly injury; rehabilitation time is extensive and return to pre-injury activity is often limited. Between 1990 and 2010 the overall age- and sex-adjusted annual incidence of Anterior Cruciate Ligament (ACL) tears in the U.S. was 68.6 per 100,000 person-years (1). A 2014 study reported 81 ruptures per 100,000 people (2). The incidence of ACL injuries among United States service members is 10 times the reported rate for the U.S. population as a whole (3). More than 50% of service members have activity limitations or are unable to return to duty following surgery. The

Use of Blood Flow Restriction + Standard of Care Physical Therapy to Improve Functional Outcomes after
Anterior Cruciate Ligament Reconstruction
PI: [name].
Institution: UAMS
Sponsor: UAMS

possibility exists that an anterior cruciate ligament tear, even when reconstructed, can lead to permanent military activity limitations and Medical Evaluation Board (MEB) (4).

Approximately 80% of ACL reconstruction surgeries are accompanied by meniscal tear and repair. Meniscal repairs require load restrictions for several weeks immediately following surgery (5). During this time, muscle atrophy and loss of strength occurs. In order to mitigate muscle atrophy and loss of strength, we propose using Personalized Blood Flow Restriction (PBFR). PBFR will adjust to the participant's current blood flow in order to keep a constant level of blood flow restriction, thus customizing blood flow restriction for each person. Though the device technology readily available, many studies have utilized a consistent cuff pressure rather than a consistent cuff flow restriction.

The use of BFR for ACL rehabilitation is gathering support. LaPrade (6) observed the greatest benefit of BFR for individuals who are non-weight-bearing for six to eight weeks and who may have more postoperative restrictions. Quadriceps girth has been preserved to contralateral standards with BFR following the non-weight-bearing period. There have been only a few studies published on BFR and ACL. Ohta, et al (7) used low-load resistance muscular training with moderate BFR after ACL reconstruction. However, their study used a standard occlusion pressure, additional home training, and the involvement of meniscal tear/repair was uncertain. Bowman, et al (8) found that BFR training strengthens muscle groups proximal, distal, and contralateral to cuff placement following ACL repair. However, their measures were not elegant and the study was not blinded. Only one study (9) evaluated physical functional outcomes, though they were self-reported. Thus, there is a need to evaluate the use of BFR after ACL surgery in a randomized, clinical trial.

2.1 Significance

Participants will attend their usual physical therapy visits and be randomized to receive PBFR or standardized rehabilitation. This use of a current and standardized clinical program and experienced physical therapists determines both suitability and clinical

Use of Blood Flow Restriction + Standard of Care Physical Therapy to Improve Functional Outcomes after
Anterior Cruciate Ligament Reconstruction
PI: [name].
Institution: UAMS
Sponsor: UAMS

translation. We propose to evaluate physical functional outcomes with a blinded tester and quantifiable measures that are standards in our hands. The goal of this pilot project is to demonstrate the potential to steepen the healing curve after ACL repair. The improved healing time will translate to an earlier return to weight bearing and the resumption of normal activities or duty. In addition to pre-test and post-test, we will incorporate two additional testing points over the length of the physical therapy sessions. This testing schedule will identify progress in functional outcome recovery over the course of rehabilitation. If successful, this rehabilitative modality may allow rehabilitation economics to be truncated and an earlier return to function. This pilot study will provide data, process refinement, and methods confirmation in preparation for a larger project submission.

3.0 Benefits and Specific Aim

There is a growing body of evidence demonstrating that the combination of blood flow restriction (BFR) with low intensity resistance exercise can induce similar gains in muscular strength and hypertrophic adaptations as moderate or high intensity resistance training (10). BFR is an attractive modality for patients after ACL reconstruction due to its efficacy with low intensity resistance exercise. The attractive aspect of PRFT with BFR is that strength and functional improvements may be garnered over a shorter period of time and more importantly, with lower training loads. The lower training load is particularly applicable to post-ACL patients with accompanying pain and diminished function and weight bearing. The ability to improve strength and function with a reduced total rehabilitation is an attractive financial and pragmatic solution in this patient population. Therefore, we propose a pilot project to determine the effects of adding PBFR to the standard of care on strength and functional outcomes after ACL reconstruction. We will compare the benefits of three times weekly standard of care including PBFR training versus standard of care rehabilitation throughout 16 weeks post ACL reconstruction.

Use of Blood Flow Restriction + Standard of Care Physical Therapy to Improve Functional Outcomes after
Anterior Cruciate Ligament Reconstruction
PI: [name].
Institution: UAMS
Sponsor: UAMS

Specific Aim: To determine the effects of PT + PBFR after elective ACL surgery on muscle mass, strength, and function.

4.0 Study Population

Up to 25 subjects of any gender or ethnicity will be enrolled with a target of n=20 for study completion.

4.1 Inclusion Criteria

1. Men and women, ages 18-34 years.
2. Scheduled to undergo elective ACL surgery at UAMS.
3. Capable of providing informed consent.
4. Willing to exercise with BFR.
5. COVID-19 negative or asymptomatic.

4.2 Exclusion Criteria

1. Any surgical indication other than ACL repair.
2. Body mass index >40.
3. Pregnant female.
4. Neurological, musculoskeletal, or other disorder that would preclude them from completing the exercise training intervention and all performance tests.
5. Hypertension as evidenced by systolic BP >150 at rest OR diastolic BP >85 at rest.
6. Heart failure as evidenced by use of prescription diuretics.
7. History of atrial fibrillation.
8. Oxygen saturation <95% on room air at rest.
9. Any other medical condition that would interfere with testing or increase one's risk of complications during exercise.
10. Currently receiving androgen (e.g., testosterone) or anabolic (e.g., GH, IGF-I) therapy.

Use of Blood Flow Restriction + Standard of Care Physical Therapy to Improve Functional Outcomes after
Anterior Cruciate Ligament Reconstruction
PI: [name].
Institution: UAMS
Sponsor: UAMS

11. Compromised vascular circulation in the legs (e.g. peripheral vascular disease).
12. History of deep vein thrombosis.
13. Varicose veins in the legs.
14. Known Sickle cell disease or trait.
15. Unwilling to avoid using protein or amino-acid supplements during participation.
16. Unwilling to avoid using BFR during prescribed post-operative physical therapy.

4.3 Subject Recruitment

Subjects will be recruited by the surgeon or their designee. Referrals will be sent to study staff via email. Study staff will contact referrals using their preferred method of communication (as per Epic) and present the study overview to them. Interested subjects will then be scheduled for Visit 1 where the informed consent process will take place in the Reynolds Institute on Aging.

4.4 Subject Compensation

Subjects will be compensated for participation as shown in the table below. They will be given a Visa @ gift card for visit 1, and be handed a UAMS check for the sum of their participation \$50 at the completion of each other study visit when their participation ends (unless they request more frequent compensation). Parking passes will be provided to all subjects for all RIOA visits at no cost to subjects.

Visit 1	\$25
Visit 2	\$50
Visit 3	\$50
Visit 4	\$50
Visit 5	\$50

5.0 Study Visits

Use of Blood Flow Restriction + Standard of Care Physical Therapy to Improve Functional Outcomes after
Anterior Cruciate Ligament Reconstruction
PI: [name].
Institution: UAMS
Sponsor: UAMS

Subjects will be required to wear a mask. If they do not have one, a mask will be provided to them by the study staff.

Visit 1: This visit will take place at the UAMS RIOA prior to surgery. At this visit, informed consent discussion will be held. Study staff will use appropriate PPE. This visit is expected to take less than about one hour. If a subject consents, their vital signs will be measured (blood pressure, oxygen saturation) while at rest for at least 10 minutes for exclusion criteria. Randomization will occur. [name] will be notified via email as to which group each enrolled subject has been randomized. He will then communicate this to the relevant physical therapists at the Col. Glenn facility.

Visit 2: This fasted visit will occur approximately 7-10 days before surgery. Subjects will be asked to fast for 8 hours, avoid caffeine and alcohol for 12 hours, and avoid strenuous exercise for 24 hours prior to this visit. Subjects will undergo body composition testing (DEXA, InBody). After a 5 minute warm up (stretching/walking/cycling as tolerated), strength testing of each leg, and 10-meter walking speed test will commence. This visit is expected to take about 1 hour.

Visit 3: This visit will take place at the UAMS RIOA approximately 8 weeks after surgery. Subjects will be asked to fast for 8 hours, avoid caffeine and alcohol for 12 hours, and avoid strenuous exercise for 24 hours prior to this visit. At this visit, a 5-minute warm up, physical, functional, and body composition testing (DEXA, InBody) will take place (see Study Calendar). Future study visits will be scheduled. This visit is expected to take about 1 hour.

Visit 4: This visit will take place at the UAMS RIOA approximately 12 weeks after surgery. Subjects will be asked to fast for 8 hours, avoid caffeine and alcohol for 12 hours, and avoid strenuous exercise for 24 hours prior to this visit. At this visit, a 5-minute warm up, physical, functional, and body composition testing (DEXA, InBody) will

Use of Blood Flow Restriction + Standard of Care Physical Therapy to Improve Functional Outcomes after
Anterior Cruciate Ligament Reconstruction
PI: [name].
Institution: UAMS
Sponsor: UAMS

take place (see Study Calendar). Future study visits will be scheduled. This visit is expected to take about 1 hour.

Visit 5: This visit will take place at the UAMS RIOA approximately 16 weeks after surgery. Subjects will be asked to fast for 8 hours, avoid caffeine and alcohol for 12 hours, and avoid strenuous exercise for 24 hours prior to this visit. At this visit, a 5-minute warm up, physical, functional, and body composition testing (DEXA, InBody) will take place (see Study Calendar). Future study visits will be scheduled. This visit is expected to take about 1 hour.

As part of PT, subject's level of pain will be ascertained using a 0-10 point scale at the onset of their PT visits. They will also be asked to complete the Fear-Avoidance Beliefs Questionnaire at some visits. The ROM of their surgical knee will be measured at certain times. In addition, progression towards UAMS' 'Return to Sport' measurements are performed and documented. Some of these data elements will be retrieved from the therapist's notes in Epic by study staff.

6.0 Blinding

The study is a single-blind, randomized, controlled trial (RCT). While participants cannot be blinded since BFR is the intervention being evaluated, key investigators and outcomes assessors will be blinded to treatment assignment, making this a single-blind RCT from the investigators' perspective.

7.0 Randomization

Subjects will be randomized 1:1 at the conclusion of Visit 1 using a randomly generated list of group designations that corresponds to subject ID.

Use of Blood Flow Restriction + Standard of Care Physical Therapy to Improve Functional Outcomes after
Anterior Cruciate Ligament Reconstruction
PI: [name].
Institution: UAMS
Sponsor: UAMS

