9.0 Outcome Measures

9.1 10-meter Walking Speed

This test is performed in a quiet, well-lit hallway. Subjects are instructed to walk as quickly as they can without running through a 20-meter course. The middle 10 meter distance is timed using stationary timer devices. Subjects will be accompanied by study staff for safety purposes but will not help the subject unless required.

Use of Blood Flow Restriction + Standard of Care Physical Therapy to Improve Functional Outcomes after
Anterior Cruciate Ligament Reconstruction
PI: [name].
Institution: UAMS
Sponsor: UAMS

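### Randomisation precedes the two effort-dependent pretests, and nothing withholds the arm from participants until those tests are done: an avoidable, conditional risk that is cheap to remove

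*Combined protocol and SAP*

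**What the plan says.** Three places agree on the order. Section 7.0 says "Subjects will be randomized 1:1 at the conclusion of Visit 1 using a randomly generated list of group designations that corresponds to subject ID". The Study Schema puts "Randomization (1:1) occurs" under Visit 1, and the Visit 1 text in section 5.0 says the same.

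Baseline measurement follows: "Visit 2: Approx. 7-10 days prior to surgery, subjects come to RIOA for baseline testing". At that visit, after the body composition scans and a warm-up, "strength testing of each leg, and 10-meter walking speed test will commence". The arms first diverge after surgery: "Prescribed physical therapy begins with or without BFR per randomization at UAMS".

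On who learns the allocation, section 5.0 sends it by email to one team member: "He will then communicate this to the relevant physical therapists at the Col. Glenn facility". It does not say when participants are told. Section 6.0 says "participants cannot be blinded since BFR is the intervention being evaluated" and blinds key investigators and outcome assessors.

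Section 10.1 fits an ANCOVA for each parameter with intervention group and the pretest, tested two-sided at 0.05. It gives the pilot's objective as obtaining data to power later studies. Section 4.0 allows up to 25 enrolled, with a target of 20 completers.

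**The concern.** ANCOVA adjustment is safe when the covariate cannot be affected by the assigned arm. Measuring the pretest before allocation guarantees that. Measuring it afterwards makes it depend on what the participant knows.

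Two Visit 2 measures are open to this. For the walk, "Subjects are instructed to walk as quickly as they can without running through a 20-meter course". MVC (section 9.2) is the best peak torque over three attempts. Someone who knows which rehabilitation they will receive might try harder or less hard on either test. Blinded assessors control how the test is run and read, not how hard the participant tries. Any arm-related shift in the pretest would pass through the covariate into the adjusted arm difference, in a direction that cannot be predicted.

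The early timing also means that anyone who leaves between Visit 1 and Visit 2 is already in the randomised set. The protocol gives no reason for allocating this early, and nothing done at Visit 2 depends on the arm.

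**Working it through.** **Step 1: order and disclosure.** The documented sequence is consent and allocation (Visit 1), pretests (Visit 2, about 7-10 days before surgery), surgery, then therapy that differs by arm. The only notification route runs from one team member to the therapists. Disclosure to participants before Visit 2 is neither stated nor excluded.

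**Step 2: outcomes exposed.** In the Study Calendar, MVC, walk, DEXA and InBody are measured at Visit 2. Stair ascent, stair descent and Y-balance are not, so they have no pretest to distort. DEXA and InBody are not effort tests. That leaves MVC and walking speed.

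**Step 3: possible size.** The plan states no SD, effect size, pre-post correlation or power, so there is no figure to reproduce.

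- From the documents: 10 per arm (20 completers, 1:1); ANCOVA with group and pretest, so df = 20 - 3 = 17; two-sided 0.05.
- Assumed: unit SDs, no true effect, pre-post slope b = 0.5 or 0.7, effort shift s = 0.1, 0.2 or 0.3 SD in one arm's observed pretest.

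Model: post = b x true baseline + error, and observed baseline = true baseline + s in one arm.

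- Expected adjusted difference = 0 - b x s, opposite in sign to the shift.
- SE with no shift = sqrt(1 - b²) x sqrt(2/10) x sqrt(1 + 1/16). At b = 0.5: 0.866 x 0.447 x 1.031 = 0.399. At b = 0.7: 0.714 x 0.447 x 1.031 = 0.329.

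Baseline-only shift, 200,000 simulated trials per scenario:

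| b | s | Absolute bias (SD) | Bias / SE | Type I error |
|---|---|---|---|---|
| 0.5 | 0.1 | 0.05 | 0.13 | 5.2% |
| 0.5 | 0.2 | 0.10 | 0.25 | 5.6% |
| 0.5 | 0.3 | 0.15 | 0.37 | 6.5% |
| 0.7 | 0.1 | 0.07 | 0.21 | 5.4% |
| 0.7 | 0.2 | 0.14 | 0.42 | 6.8% |
| 0.7 | 0.3 | 0.21 | 0.63 | 9.2% |

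Bias / SE uses the simulated SE, which a shift raises slightly (to at most about 0.405 and 0.334). With no shift, type I error is 5.0%. Repeat runs agreed to within about 0.2 percentage points.

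**Step 4: does the shift persist?** Participants certainly know their arm at Visits 3 to 5, so a baseline-only shift is just one possibility.

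- Same shift at pretest and post-test: bias = s - b x s = (1 - b) x s. This runs from 0.3 x 0.1 = 0.03 to 0.5 x 0.3 = 0.15 SD, with type I error of 5.1 to 6.4%.
- Shift at post-test only, which is what could remain after the fix: bias = s = 0.10 to 0.30 SD, with type I error of 5.6 to 13.9%.

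**Step 5: effect on the pilot's planning inputs.** Adding a constant to one arm's pretest changes neither the within-arm SDs nor the pre-post slope. Only the arm contrast moves.

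**Step 6: losses before Visit 2.** Section 4.0 allows 25 - 20 = 5 losses without saying when they occur. If 1 or 2 fall between Visits 1 and 2 (assumption), that is 1/25 = 4% or 2/25 = 8% of those randomised. They would normally lack post-tests as well as pretests, so they would be absent from the ANCOVA in any case.

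**The case against.** A reader might infer from section 6.0 that participants know their arm when they do the pretests. The documents do not support this. That section ties the lack of blinding to BFR being the intervention, BFR starts only after surgery, and nobody is instructed to tell the participant at Visit 1. This objection stands in full: without disclosure before Visit 2 the bias is zero. What remains is that no safeguard is written down.

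The second objection is that the figures follow from the assumptions. That is also true. At a slope of 0.3 the baseline-only type I error stays at about 5%; at a slope of 0.8 with a 0.5 SD shift it reaches about 27%. No section supports any particular slope or shift.

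The third is that moving randomisation need not reduce total effort bias. If the shift is stable over time, a shared pretest shift partly cancels the post-test shift, and removing it could leave a larger error. This stands as a limit on what the change can achieve. It is not a reason to keep the covariate exposed to the arm: the cancellation would be accidental, and post-test effort bias arises from unblinded treatment under either timing.

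A reader might also infer that later randomisation would recover data for the ANCOVA. It would not, because early leavers would normally have no post-test either. In addition, inclusion criterion 4 and exclusion criterion 16 screen for willingness to exercise with BFR and to go without it, which limits arm-driven withdrawal.

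**Conclusion.** The order of events is explicit, and the absence of any withholding rule is confirmed. The consequence is conditional: it needs participants to learn their arm before Visit 2 and to change their effort because of it, and neither is documented. Reading the plan as already biased goes further than the text allows.

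If both conditions held, only the MVC and walking-speed contrasts would be affected. On the assumed inputs, the bias is 0.05 to 0.21 SD (0.13 to 0.63 standard errors) for a baseline-only shift, or 0.03 to 0.15 SD if the shift persists. Four of the six baseline-only scenarios keep type I error at or below about 6.5%. The variances and slopes that the pilot is meant to supply are not affected by a constant shift.

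Later allocation guarantees an arm-independent pretest and a cleaner randomised set. It does not give protection from effort bias at Visits 3 to 5. This is a cheap improvement of minor to moderate severity.

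**What to change.** Keep consent and vital-sign screening at Visit 1. Change section 7.0 to: *Subjects will be randomized 1:1 after Visit 2 testing is complete and before the first PT session at which the groups differ.* Move the randomisation and notification sentences in the Visit 1 text of section 5.0 to after Visit 2, and move the randomisation line in the Study Schema to match. Keep the existing list and notification route. State that allocation is carried out by someone other than the blinded outcome assessors.

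If the timing must stay, add one sentence: *Subjects will not be told their group until Visit 2 testing is complete.* This closes the disclosure gap but leaves early leavers in the randomised set.

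The cost is wording in three places, with no added visit or test. There are three downsides:

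- Therapists get shorter notice, though allocation at the end of Visit 2 still leaves about 7-10 days before surgery.
- Allocation sits closer in time to the assessors whom section 6.0 requires to be blinded, so the two must be kept apart.
- Subjects whose surgery is cancelled after Visit 2 remain in the randomised set. Allocating after surgery would avoid that, but no study visit is scheduled between surgery and the first therapy session.
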